6.2. Screening and Baseline Assessment

6.2.1. Diagnosis of HAT

The mobiliser of the mobile team will inform the communities in the villages of the HAT screening activities, as is usually the case (see Section 14.1 Information of Communities; p 78). Specific information concerning the study should be provided to the community, i.e. a brief description of the aim of the study, explanation of the process for collecting informed consent, duration and importance of follow-up.

HAT case detection may be carried out by the mobile team.

A physical examination and, potentially, tests may be performed to collect sufficient information to suggest a diagnosis of late-stage HAT. Whenever possible, CSF sampling will be performed at the investigational centre, or by the mobile team of the National HAT Control Programmes (see Section 4.1. Enrolment/Inclusion Procedures; p 33).

6.2.2. Pre-screening and Screening

The following assessments will be performed to confirm the diagnosis of HAT, to collect historical safety data and to check the inclusion and exclusion criteria.

- Sampling to test for trypanosomes in the blood using Woo test/CTC, thick and thin blood smears, mAECT and mAECT-BC with INRB kits, as well as in lymph using microscopic examination of fresh lymph node aspirate;
- CSF sampling for diagnosis of late-stage HAT based on WBC and detection of trypanosomes using Fuchs-Rosenthal/Fast-Read 102® counting chamber and Modified Single Centrifugation (MSC) with INRB kits;
- Collection of full medical history, with special attention to HAT;
- Demographic data and prior treatment;
- Karnofsky Performance Score, body weight, height and vital signs including body temperature, blood pressure, heart rate and respiratory rate;
- Screening for malaria using RDT and/or thick blood smear;
- Review of inclusion and exclusion criteria;

- Assessment of laboratory safety parameters (see Appendix 3 Laboratory Tests; p 96) – whenever possible, laboratory tests will be performed on fasting patients:
 - o Haemoglobin
 - o Haematocrit²
 - Haematology: WBC, platelet count
 - Biochemistry: albumin (ALB), alkaline phosphatase (ALP), alanine aminotransferase (ALAT), aspartate aminotransferase (ASAT), blood urea nitrogen (BUN), chloride (Cl-), creatinine (CRE), glucose (GLU), potassium (K+), sodium (Na+), calcium (Ca2+), total bilirubin (TBIL), bicarbonates (tCO₂), and total protein (TP)
 - Urine analysis, i.e. WBC, pH, protein, urobilinogen, blood, nitrites, glucose, ketone bodies and bilirubin
- Digital ECG recording (CarTouch®). The tracings will be uploaded to the e-CRF. Each upload of an ECG tracing will be accompanied by a request for centralised reading by the cardiologist. This will be recorded in the e-CRF and will be available for consultation by the Investigator.

6.2.3. Baseline Assessment

The following assessments will be performed before randomisation to assess the patient's baseline status just before the start of treatment. The assessments will also provide confirmation of the patient's eligibility to participate in the study, just before randomisation:

- Review of inclusion and exclusion criteria
- Vital signs, including body temperature, blood pressure and heart rate
- Verification of clinical signs and symptoms of HAT
- Physical and neurological examinations
- Collection of concomitant treatment
- Urine pregnancy test for women of child-bearing potential
- Laboratory safety assessments (see Appendix 3 Laboratory Tests; p 96)
 whenever possible, all laboratory tests will be performed on fasting patients:
 - Haemoglobin
 - Haematology: WBC, platelet count
 - Biochemistry: albumin (ALB), alkaline phosphatase (ALP), alanine aminotransferase (ALAT), aspartate aminotransferase (ASAT), blood urea nitrogen (BUN), chloride (CI-), creatinine (CRE), glucose

² Only patients at sites where PK sampling will take place.

(GLU), potassium (K+), sodium (Na+), calcium (Ca2+), total bilirubin (TBIL), bicarbonates (tCO₂) and total protein (TP)

- Urine analysis, i.e. WBC, pH, protein, urobilinogen, blood, nitrites, glucose, ketone bodies and bilirubin
- Digital ECG recording (CarTouch®): triplicate tracings to assess QT interval. The tracings will be uploaded to the e-CRF for specific analysis of QT interval.
- If the assessments mentioned in Section 6.2.2, i.e. haemoglobin, haematology, biochemistry and urine analysis, were performed within 4 days prior to the first administration, the findings will be considered as baseline values and the tests will not be repeated at the Baseline Assessment.

A treatment pack will be assigned to each randomised patient using the internetbased randomisation process accessible via the e-CRF. Patients will receive treatment over 10 days in the hospital/investigational centre.

6.3. Assessments during Hospitalisation

6.3.1. Efficacy, Clinical Signs and Symptoms

Patients will be questioned on a daily basis with regard to potential adverse events during hospitalisation and then at each subsequent visit (see Section 6.5 Safety Assessments, Definitions and Reporting of Adverse Events; p **Error! Bookmark not defined.**).

- Physical examination and neurological assessment, including signs and symptoms of HAT, will be performed prior to treatment intake (D-1/D1), and on D5, D8, D11 (EOT visit) and D18 (EOH visit, between D13 and D18)
- Testing for *T.b. gambiense* in blood, lymph and CSF at the EOT visit (D11).

6.3.2. ECG Recordings

ECG recordings will be performed at the following timepoints:

To ensure the patient's safety

- At the baseline assessment: a single ECG tracing will be analysed by the cardiologist to assess potential rhythm or conduction disorders and to assist the Investigator in screening patients.
- On D2, D3 and D4 prior to dosing in the fexinidazole group (along with the triplicate ECG tracings on D4H23): a single ECG will be analysed by the Investigator to check the QTcF interval (QT interval corrected using Fridericia's formula), calculated automatically. If the value for the QTcF

is higher than 500 ms, a second ECG tracing must be collected after a 10-to-20 minute rest. If the value is confirmed, the patient must be withdrawn from the study, and no further doses of fexinidazole are to be administered. The ECG tracings will not be reviewed systematically by the cardiologist.

• During hospitalisation and the follow-up period, additional ECG tracings may be collected at the discretion of the Investigator.

To assess QT interval

- Triplicate ECG tracings, 2 minutes apart, will be recorded at the following timepoints:
 - At the baseline assessment for all patients
 - In patients in the fexinidazole group:
 - on D4 4 hours after intake of the IP;
 - on D4H23, i.e. one hour before intake of the IP on D5, this ECG should also be used for the patient's safety assessment prior to IP administration;
 - on D10 between H2 and H3 after intake of the IP.
 - In patients in the NECT group:
 - on D7 between H2 and H3 after the morning intake of NECT, i.e. within one hour after the end of the infusion of eflornithine;
 - on D10 between H2 and H3 after the morning intake of NECT, i.e. 2-3 hours after intake of nifurtimox.

Repeat ECG

 If the cardiologist issues an alert over the last ECG examination, related to prolonged QT interval or to any aspect of the ECG morphology, the Investigator will collect a repeat ECG recording at the EOH visit, prior to discharge. If the alert is issued again at the EOH, the Investigator must collect a repeat ECG recording at the M3 follow-up visit.

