Study Objectives	 The objective of the study is to assess the efficacy and safety of an oral regimen of fexinidazole, once daily for 10 days, as compared to NECT in the treatment of late-stage sleeping sickness due to T.b. gambiense. Primary Objective To demonstrate that the success rate at 18 months after the
	end of treatment is in favour of fexinidazole, or that the difference as compared to the success rate with NECT is acceptable. Secondary Objective
	 To compare the time course of the failure rate with fexinidazole and NECT from the end of treatment visit to 24 months.

1

Г

	 To compare the safety of fexinidazole with that of NECT in the treatment of late-stage sleeping sickness due to T. b. gambiense. To assess concentrations of fexinidazole and its metabolites in the plasma and cerebrospinal fluid, and the correlations
	between the concentration and the efficacy and safety of fexinidazole.
	 To compare the pharmacodynamic impact of fexinidazole and of NECT on QT/QTcF interval.
	Exploratory Objectives
	 To validate the predictive value of three logistic models for treatment success at 18 months.
	 To compare the efficacy of fexinidazole to that of melarsoprol, eflornithine and NECT using historical data as comparators.
Primary	Efficacy
Endpoint	Outcome, i.e. either success or failure, of treatment assessed at the test-of-cure visit, 18 months after the end of treatment, based on adapted WHO criteria (55).
Secondary	Efficacy
Endpoints	Outcome, i.e. either success or failure, of treatment assessed at each visit between the end of treatment and 24 months.
	Safety
	Occurrence of adverse events, including laboratory or ECG abnormalities during the observation period, i.e. from D1 to D8, and occurrence of serious adverse events between the first treatment intake and the end of the follow-up period, i.e. 18 months. Long-term safety will be assessed up to 24 months.
	Pharmacokinetics
	Pharmacokinetic analyses will be performed on all patients in the fexinidazole group using serial dry blood spots and one dry cerebrospinal fluid spot.
	Electrocardiogram (ECG)
	Categories of QT/QTcF and changes at various timepoints.
Exploratory	Surrogate Efficacy Endpoint
Endpoint	The surrogate endpoint is the actual or predicted outcome (using logistic models, if the outcome is missing) at 18 months, based on the outcome at the last visit that took place at 6 months or later

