Adverse events will be graded according to the National Cancer Institute (NCI) Common Toxicity Criteria for Adverse Events (CTCAE), Version 4.03.

- Occurrence of adverse events, all grades combined, during the observation period, i.e. from D1 to D8, including:
 - any worsening of the clinical symptoms listed among the signs and symptoms to be checked prior to inclusion,
 - laboratory abnormalities \geq grade 2,
- Occurrence of any adverse events ≥ grade 3 during the observation period,
- Occurrence of any treatment-related adverse events, ≥ grade 3 and all grades combined, during the observation period,
- Occurrence of any serious adverse events between the first treatment intake and the end of the follow-up period (18 months), and between Month 18 and Month 24.

Potentially significant ECG abnormalities will be reported after centralised ECG review.

Pharmacokinetic Endpoints

PK sampling in patients in the fexinidazole group will only be performed at the first 6 investigational sites.

Concentrations of fexinidazole, M1 and M2 in whole blood and in CSF, as well as PK parameters derived from a population PK model.

- Samples of whole blood will be collected using dry blood spot (DBS) testing on a finger-prick sample at the following timepoints:
 - o on Day 8, 3 hours and 15 minutes after intake of the IP,
 - o on Day 9, 3 hours after intake of the IP,
 - $\circ~$ on Day 10, 3 hours and 7 hours and 15 minutes after intake of the IP,
 - o on Day 11, 24 hours after intake of the IP,

- o on Day 12, 48 hours after intake of the IP.
- Lumbar puncture will be performed on Day 11, 24 hours after intake of the IP for the EOT efficacy assessment. A dry CSF spot will be collected at the same time for PK analyses for all patients until the end of July 2013.

ECG Endpoints

Triplicate ECG tracings will be recorded at 2-minute intervals to assess QT interval at the following timepoints:

- At baseline for all patients
- Thereafter:
 - in patients in the fexinidazole group: on Day 4, 4 hours (H4) after intake of the IP, on Day 4 Hour 23, and on Day 10 2-3 hours after intake of the IP,
 - in patients in the NECT group: on Day 7 2-3 hours after treatment intake in the morning and on Day 10 2-3 hours after treatment intake in the morning.

Triplicate ECGs and a safety ECG will be collected for different purposes and will be analysed separately (see Section 6.3.2 ECG Recordings; p 47).

3. Study Design

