6.5.1. Definition of AE

An AE is defined as any untoward and unintended medical occurrence (sign, symptom or disease), including a clinically significant abnormal laboratory or ECG finding, or worsening of any pre-existing condition during the study, whether or not it is considered to be study related.

Any abnormal laboratory result on haematology, biochemistry or urine analysis will be reported as an AE if it occurs or worsens after the start of the study treatment, and if the CTCAE grade is > 1, unless it is associated with a previously reported clinical event.

The Investigator or appropriate study personnel will examine any patient who experiences an AE as soon as possible. The Investigator will do whatever is medically necessary for the patient's safety and well-being. The patient will remain under observation as long as s/he is receiving study treatment and up to the last day of the observation period (between D13 and D18), or longer if medically indicated in the opinion of the Investigator. All AEs observed or reported following administration of the study treatment will be followed until resolved or until the Investigator considers them to be "chronic" or "stable".

All identified AEs will be recorded in the appropriate AE section of the e-CRF using concise medical terminology, and avoiding vague, ambiguous or colloquial language. SAEs will be reported by telephone, Short Message Service (SMS) or email to Swiss TPH (see Section 6.5.5 Requirements for AE Reporting; p 54).

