8.2. Rules for Definitive Discontinuation of Treatment

The Investigator will discontinue the study treatment in the following cases:

- Severe skin reaction
- ALAT or ASAT exceeding 8 x ULN
- ALAT or ASAT exceeding 3 x ULN associated with total bilirubin > 2 x ULN
- ALAT or ASAT exceeding 3 x ULN accompanied by fatigue, nausea, vomiting, right upper quadrant pain or tenderness, fever, rash, and/or eosinophilia (>5%)
- pre-dose QTcF measurement ≥ 500 ms on D2, D3, D4 or D4H23, confirmed by a second ECG recorded after at least a 10-20 minute rest
- Any condition that, in the opinion of the Investigator, requires treatment discontinuation for medical reasons.

If a patient is withdrawn from the study before the end of treatment, the physician will make all necessary arrangements to ensure that s/he receives the appropriate treatment for the condition in question.

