Appendix 4 - Tables

Table 4 – Schedule of Study Procedures

Protocol-planned procedures and forms to be completed	Pre-screening and Screening	Baseline	e Treatment period										End-of-Treatment Visit until End-of- Hospitalisation Visit			Follow-up period (months)
Timepoint	D-15 to D-1	D-4 to D- 1	D1	D2	D3	D4	D5	D6	D7	D8	D9	D10	D11	D12	D13-D18	Week 9 ³ 3 – 6 – 12 – 18 -24 months
Detection of parasite in blood and/or lymph	Х												х			х
Lumbar puncture (parasite and white blood cells in CSF)	x												х			x ¹
Informed consent (before any additional medicines or study-specific procedures)	×	Check														
Pretreatment of helminthiasis (+ 3-day recovery period)	x															
Rapid diagnostic test and/or thick blood smear for malaria	Х															
Pretreatment of malaria if necessary (+ 3-day recovery period)	x															
Karnofsky score	Х	Check														х
Safety ECG	Х	Check														
Safety ECG (fexinidazole group only)				х	х	х										
Urine pregnancy test		х													х	x (only at 3 months)
Inclusion and exclusion criteria	Х	х														
Randomisation		х														
Demographic data	Х															
Medical history	Х															х
Signs and symptoms of HAT		х													х	х
Vital signs	Х	х					х			х			х		х	х
Physical examination		х					х			х			х		х	х
Neurological examination		х					х			х			х		х	х
Haematology and biochemistry	Х	х					х			х			х			x (only at Week 9)
Haematocrit ²	Х															
Urine analysis	Х	х											х			

¹ Except for 3-month follow-up visit unless the patient presents with clinical symptoms or signs of HAT.

² Only for patients at sites where PK sampling is performed.

³ Only at Week 9 after D1, perform sampling for haematology and biochemistry, physical examination and neurological examination.

Protocol-planned procedures and forms to be completed	Pre- screening and Screening	Baseline		Treatment period						End-of-Treatment Visit until End-of-Hospitalisation Visit			Follow-up period (months)			
Timepoint	D-15 to D-1	D-4 to D-1	D1	D2	D3	D4	D5	D6	D7	D8	D9	D10	D11 (EOT)	D12	D13-D18	Week 9 3 – 6 – 12 – 18 -24 months
Triplicate ECGs –fexinidazole group		x				x D4H4 D4H23						x D10H2-H3				
Triplicate ECGs – NECT group		x							x D7H2- H3			x D10H2-H3				
Administration of fexinidazole			х	х	х	х	х	х	х	х	х	х				
Administration of NECT			х	х	х	х	х	х	х	х	х	х				
Treatment-related adverse events			х	х	х	х	х	х	х	х	х	х	х	х	х	

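### Scheduled post-baseline ECGs fall on six occasions under fexinidazole and two under NECT, and the AE and discontinuation tables in Section 9.9 make no allowance for it

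*Protocol*

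**What the plan says.** **ECG schedule.** Section 6.3.2 places single safety ECGs "On D2, D3 and D4 prior to dosing in the fexinidazole group". The same arm has triplicates "on D4 4 hours after intake of the IP", then "on D4H23, i.e. one hour before intake of the IP on D5", and again on D10 between H2 and H3. For the comparator, Section 2.2.2 (ECG Endpoints) has triplicates "in patients in the NECT group: on Day 7 2-3 hours after treatment intake in the morning" and on D10. Table 4 agrees and restricts the D2-D4 safety ECGs to the fexinidazole group.

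**Discontinuation rule.** Section 8.2 stops treatment for a confirmed "pre-dose QTcF measurement ≥ 500 ms on D2, D3, D4 or D4H23". None of these days carries a scheduled ECG in the NECT arm.

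**AE definition and analysis.** Section 6.5.1 defines an AE as "including a clinically significant abnormal laboratory or ECG finding". The safety endpoint in the Protocol Summary reads "Occurrence of adverse events, including laboratory or ECG abnormalities during the observation period". Comparing safety between the arms is a secondary objective (Section 2.1.3). Section 9.9 presents AE incidence with 95% confidence intervals, and AEs leading to discontinuation, by treatment group. It does not limit ECG-detected events to occasions that both arms share.

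**The concern.** An AE that can be found only by recording an ECG is counted only if an ECG is recorded. One arm is examined more often and much earlier, so the two AE proportions do not rest on equal opportunity for detection. The same holds for discontinuations triggered by the scheduled QTcF checks. Daily AE questioning and the laboratory days are the same in both arms, so the problem is confined to ECG-derived events.

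At stake are the estimates used to describe relative safety. The tilt runs against fexinidazole, and an early ECG effect of NECT could go unseen.

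**Working it through.** **Count of scheduled post-baseline occasions** (Sections 2.2.2, 6.3.2 and 8.2; Table 4)

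- Fexinidazole: D2, D3, D4 pre-dose, D4H4, D4H23, D10 = 6 occasions; tracings 3 × 1 + 3 × 3 = 12.
- NECT: D7, D10 = 2 occasions; tracings 2 × 3 = 6.
- Before D7: 5 against 0.
- Scheduled QTcF checks under the discontinuation rule: 4 against 0.
- Triplicates only: 3 against 2.

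The protocol gives no figure for the effect of this imbalance, so there is none to reproduce.

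**Illustration.** Let p be the chance of a reportable ECG finding per occasion, the same in both arms. The documents do not give p, so a range is assumed. With independent occasions, the chance of at least one finding in k occasions is 1 − (1 − p)^k.

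| p | k = 6 | k = 2 | ratio 6 vs 2 | k = 3 | ratio 3 vs 2 |
|---|---|---|---|---|---|
| 1% | 5.9% | 2.0% | 2.94 | 3.0% | 1.49 |
| 2% | 11.4% | 4.0% | 2.88 | 5.9% | 1.49 |
| 5% | 26.5% | 9.8% | 2.72 | 14.3% | 1.46 |

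At p = 1% with 260 and 130 patients, this is about 15.2 against 2.6 patients with at least one finding, with no true difference.

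**Correlated occasions.** Findings in one patient will tend to repeat. In a beta-binomial model with intraclass correlation r, a = p(1 − r)/r and b = (1 − p)(1 − r)/r. The chance of no finding in k occasions is the product of (b + i)/(a + b + i) for i = 0 to k − 1. Over p = 1-5%:

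- r = 0.3: ratio 1.96 to 1.89 for six vs two; about 1.3 for three vs two.
- r = 0.6: ratio 1.49 to 1.46 for six vs two; about 1.2 for three vs two.

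**Very rare events.** Section 1.7 reports one 60 ms increase from baseline in more than 4000 ECGs. That was in healthy volunteers and is a different event, so it is only indicative. At p = 1/4000 with independent occasions:

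- at least one finding: 260 × [1 − (1 − 1/4000)^6] = 0.39 patients against 130 × [1 − (1 − 1/4000)^2] = 0.06;
- four pre-dose checks: 260 × [1 − (1 − 1/4000)^4] = 0.26 patients.

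The ratio stays near 3, but less than one patient is involved.

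**The case against.** Several counter-arguments have force.

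- **Much is already shown by timepoint.** Section 9.9 presents ECG abnormalities for each timepoint within each group, and Section 9.10 gives QT/QTcF categories at the various timepoints. Section 2.2.2 analyses triplicate and safety ECGs separately. This stands for the ECG and QT tables. A reader might infer that the QT/QTcF comparison itself is biased because categories would be taken at any time over three against two triplicates. The protocol plans no such analysis, and it leaves ECG data conventions to a separate SAP.
- **The D2-D4 tracings are narrow.** They check an automated QTcF against a 500 ms threshold with confirmation, in patients screened for QTcF at entry. The cardiologist does not review them systematically. Section 2.2.2 reports potentially significant abnormalities after central review, and for that set three against two is nearer the truth than six against two. This lowers the likely size. It does not take an investigator-reported ECG event out of the AE tables.
- **NECT patients are not unmonitored.** Discretionary ECGs are allowed, and Section 8.2 lets the investigator stop treatment for any medical reason. A reader might infer that ECG-triggered discontinuation is impossible under NECT. The documents support only that no scheduled check exists there. Unscheduled tracings do not equalise opportunity.
- **No test depends on it.** This is true: the AE analysis is descriptive, so estimates and intervals are affected, not a decision rule.

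A reader might also conclude that the arms should be compared only at D10, the one shared time. That does not follow. Under Section 5.2 eflornithine lasts 7 days, so at D10 NECT patients receive nifurtimox alone. Fexinidazole patients are then past the loading days. A D10-only comparison would drop the loading-dose readings and the only reading taken just after an eflornithine infusion.

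The extra early monitoring is understandable given the QTcF signal in Section 1.7 and is not in question.

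**Conclusion.** The point holds for two sets of tables: overall AE incidence and AEs leading to discontinuation. Scheduled ECG opportunity is six occasions against two, and four QTcF discontinuation checks against none. Nothing in Section 9.9 allows for either.

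The direction is clear for ECG-detected events when per-occasion rates are equal. The size is not known. The ratio is about 2.7-2.9 for independent occasions at 1-5%, about 1.5-2.0 with correlation of 0.6 to 0.3, and about 1.2-1.5 on triplicates alone. These rates and correlations are assumptions. If reportable findings are as rare as the healthy-volunteer figure suggests, AE totals would move by less than one patient. The six-against-two ratio does not describe discontinuations, where the scheduled contrast is four against none.

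This is a cheap improvement in reporting. It is not a flaw in the ECG schedule or in the planned QT analysis.

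**What to change.** In Section 9.9, present overall AE incidence and AEs leading to discontinuation by arm in two versions: all events, and all events except those detected only through scheduled protocol ECGs. State the unequal schedule (six against two occasions; QTcF discontinuation checks in one arm only) beside those tables.

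Keep the QT/QTcF comparison by timepoint as planned, and do not restrict it to D10.

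Cost: additional tables and a flag identifying ECG-triggered AEs and discontinuations. No ECG is added or removed, and no clinical rule changes.

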8.1. Rules for Temporary Interruption of Treatment

Temporary interruption of treatment will not necessarily lead to withdrawal of the patient from the study. In some cases, treatment may be interrupted for a maximum of one day, i.e. one missed dose of fexinidazole or 3 missed doses of NECT, and treatment will therefore be delayed. Treatment may be reintroduced at the discretion of the Investigator responsible for the patient. One additional day of treatment will be added to make up for the missed dose (or doses as concerns NECT). The patient should continue the visits and study procedures as planned, taking into account the delay. The reasons for interrupting treatment must be recorded in the appropriate source documents and e-CRF.

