8.3. Patient Withdrawal from the Study and Replacement of Patients

A patient may be withdrawn from the study in the following cases:

- withdrawal of consent by the patient or his/her legal representative,
- study termination by the Sponsor.

If the patient or his/her legal representative withdraws his/her consent, no further evaluations will be performed, with the exception of safety data, which must be collected whenever possible.

If a patient decides to withdraw from the study, the reason must be recorded in the e-CRF. If a patient is withdrawn from the study due to an AE, all measures must be taken as needed to clearly document the outcome of the AE.

Data collected prior to withdrawal of the patient will be taken into account in the PK, efficacy and safety analyses.

Patients withdrawn from the study will not be replaced.

If a patient is lost to follow-up for reasons related to armed conflict, after several unsuccessful attempts have been made to contact him/her, and if no data are available after the treatment period, the patient will be removed from the primary analysis and another patient will be included.

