8.4. Patients Lost to Follow-up

If a patient does not attend a protocol-planned visit, all necessary measures must be taken to contact him/her. In all cases, all necessary measures must be taken to document the outcome of the patient's condition, if possible.

9. Data Analysis and Statistical Methods

A draft of the full Statistical Analysis Plan (SAP) will be prepared prior to conducting the first FA. It will provide a more detailed description of the statistical methods. The SAP will be reviewed and, if necessary, amended prior to final database lock.

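### Sections 6.3.2 and 8.2 give different QTcF limits (above 500 ms; 500 ms or more) and different consequences (study withdrawal; treatment discontinuation) for the same pre-dose ECGs

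*Protocol*

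**What the plan says.** Protocol section 6.3.2 (ECG Recordings) requires a single safety ECG in the fexinidazole group before dosing on D2, D3 and D4, and uses the D4H23 tracing for the same purpose before the D5 dose. If the automatic QTcF "is higher than 500 ms, a second ECG tracing must be collected" after a 10-to-20 minute rest. The consequence is: "If the value is confirmed, the patient must be withdrawn from the study, and no further doses of fexinidazole are to be administered".

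Section 8.2 opens with "The Investigator will discontinue the study treatment in the following cases" and lists "pre-dose QTcF measurement ≥ 500 ms on D2, D3, D4 or D4H23, confirmed by a second ECG" after a comparable rest. Its closing sentence begins: "If a patient is withdrawn from the study before the end of treatment, the physician will make all necessary arrangements".

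The neighbouring sections bear on how these rules are read:

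- 8.1: "Temporary interruption of treatment will not necessarily lead to withdrawal of the patient from the study". It adds that visits continue after an interruption.
- 8.3 lists two cases for withdrawal from the study, namely "withdrawal of consent by the patient or his/her legal representative" and termination by the Sponsor. A later sentence nevertheless speaks of patients withdrawn because of an AE.
- 8.4, for patients who miss a planned visit: "In all cases, all necessary measures must be taken to document the outcome".

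**The concern.** A cardiac stopping rule should have one limit and one consequence. Here each is given in two forms, for the same ECGs and the same confirmation step.

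The consequence matters more than the limit. Section 8.1 states that visits go on after a temporary interruption, but no matching sentence covers a definitive stop. A site that takes 6.3.2 at its word could remove the patient from the scheduled visits. A site that works from 8.2 would stop the drug and could reasonably keep the visits.

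The patients concerned have had at most four of ten doses for a disease that is usually fatal untreated, so relapse follow-up is especially needed. They are also the patients with the most marked QTcF findings, and the effect on QT/QTcF is a secondary objective (2.1.3). The rule applies to fexinidazole alone, so any follow-up lost through it would fall on one arm of an open-label comparison.

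**Working it through.** **1. The two rules side by side**

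| Item | 6.3.2 | 8.2 |
|---|---|---|
| Timepoints | D2, D3, D4, D4H23 | D2, D3, D4, D4H23 |
| Limit | above 500 ms | 500 ms or more |
| Confirmation | repeat ECG after rest | repeat ECG after rest |
| Drug | stopped | stopped |
| Study participation | withdrawal ordered | withdrawal not ordered |

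**2. Limit.** Above 500 ms both rules act; below 500 ms neither does. They part only at exactly 500 ms. There 8.2 needs a second ECG to confirm the value, and 6.3.2 does not order that second ECG.

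**3. Consequence.** For every confirmed value above 500 ms, 6.3.2 adds an instruction that 8.2 lacks.

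**4. Exposure at the time of a stop** (regimen from 5.1). Full course: 4 × 1800 + 6 × 1200 = 14,400 mg.

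| Stop at | Doses taken | mg received | Share of course |
|---|---|---|---|
| D2 | 1 | 1800 | 12.5% |
| D3 | 2 | 3600 | 25% |
| D4 | 3 | 5400 | 37.5% |
| D4H23 | 4 | 7200 | 50% |

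**5. Scoring in the primary analysis.** The patient has been dosed and so stays in ITT (9.4). A missing Month-18 outcome is a failure unless the probable-success criteria are met (9.2). Rescue treatment is a failure (9.8.1). The most that study withdrawal can do is turn a would-be success into a failure.

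**6. Size.** Inputs: 260 and 130 patients, success rates 89% and 94% (9.1), margin 13 points (9.8.1). The number of patients re-scored, k = 0 to 3, is an assumption, because the protocol gives no rate for this event. The lower bound is the unpooled Wald form:

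d − z × √[p_F(1 − p_F)/260 + p_N(1 − p_N)/130], with p_F = 0.89 − k/260, p_N = 0.94 and d = p_F − p_N.

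For k = 0 the standard error is √(0.0979/260 + 0.0564/130) = 0.02847, so the bound at z = 1.96 is −5.00 − 5.58 = −10.58 points. The last column uses z = 2.178, the two-look Pocock value; 9.11 names the Pocock approach but gives no critical value.

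| k | p_F | d (points) | Bound, z = 1.96 | Bound, z = 2.178 |
|---|---|---|---|---|
| 0 | 89.00% | −5.00 | −10.58 | −11.20 |
| 1 | 88.62% | −5.38 | −11.00 | −11.63 |
| 2 | 88.23% | −5.77 | −11.43 | −12.06 |
| 3 | 87.85% | −6.15 | −11.85 | −12.48 |

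Every bound stays above −13.

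**The case against.** The best defence is that the protocol uses its terms loosely and that the two sections agree on what matters most at the bedside: above 500 ms, fexinidazole stops. Section 8 as a whole is titled as withdrawal criteria, and the closing sentence of 8.2 speaks of withdrawal from the study during treatment. The list in 8.3 is permissive, and the same section contemplates withdrawal for an AE; under 6.5.1 a clinically significant ECG finding is an AE. The absence of QTcF from that list is therefore weak evidence. A reader might infer that 8.2 means stopping treatment and nothing more, but 8.2 does not say so. What stands is that 8.2 does not order study withdrawal and 6.3.2 does.

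A reader might also infer that 6.3.2 ends all follow-up. The documents do not support that. Section 8.3 bars further evaluations, safety data apart, only when consent is withdrawn. SAEs are collected to 24 months (6.5.4), and SAEs and possibly related events are followed after participation ends (6.5.9). Section 8.4 asks for outcomes to be documented after missed visits. Section 9.2 asks for every effort to reach patients at 18 months or later and uses outcomes learned off schedule. These provisions soften the instruction in 6.3.2, but none tells a site whether the scheduled visits go on.

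The event is also likely to be rare. QTcF of 450 ms or more on two ECGs excludes a patient at entry (4.3). Section 1.7 reports prolongations usually near 30 ms in healthy volunteers, with one 60 ms increase in more than 4000 recordings. At exactly 500 ms a site can satisfy both sections by applying 8.2. All of this limits the size of the problem; it does not reconcile the two texts.

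**Conclusion.** The inconsistency is real and minor. The limits differ only at exactly 500 ms. The consequences differ for every confirmed value above it, with the reservation that withdrawal is used imprecisely in 8.2 and 8.3.

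The primary conclusion is not threatened, and a reader should not infer bias in the non-inferiority result from this point. Month-18 scoring is already fixed, and one re-scored patient is worth 0.38 points. Moving three takes the lower bound from −10.58 to −11.85 (z = 1.96), or from −11.20 to −12.48 (z = 2.178). These figures assume planned group sizes, the planning success rates, 0 to 3 affected patients, and that each would otherwise have been a success. If such a patient received another HAT treatment counted as rescue, the score would be failure either way and the shift would be zero.

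What is at stake is consistent conduct of a cardiac safety rule, and relapse and QT follow-up in a few under-dosed patients in one arm.

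**What to change.** - Use 500 ms or more as the limit in both 6.3.2 and 8.2, so that the repeat ECG is ordered at the value where 8.2 needs it.
- In 6.3.2, replace withdrawal from the study with definitive discontinuation of study treatment according to 8.2.
- State in 8.2 and 8.3 that a safety stop of treatment does not by itself end participation: safety follow-up, any repeat ECGs and the M3 to M24 visits continue unless consent is withdrawn.
- Do not make the D11 lumbar puncture automatic for these patients. Someone stopped between D2 and D5 may be in the middle of another HAT treatment by D11, so it should be done only if clinically appropriate.

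The cost is wording in three sections and a memo to sites. No visits are added, because the schedule already covers these patients.
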